Approximately 1060 subjects will be randomized to either tezepelumab or placebo (1:1) globally from about 400 sites. The subjects will be stratified by region and age (adult/adolescents). Since the primary analysis of the primary endpoint will include all available data, including after treatment discontinuation, no need is envisaged to adjust the number of subjects planned to be randomized in order to obtain a number of evaluable subjects.

Treatments and treatment duration:

The study will consist of a screening/run in period between 5-6 weeks, a treatment period of 52 weeks and a post-treatment follow-up period of 12 weeks. Subjects will be randomized in a 1:1 ratio to either 210 mg of tezepelumab or matching placebo both administered Q4W SC. During the treatment period, IP will be administered from Day 0 until week 48. No IP will be administered at week 52. Subjects that complete the 52-week study visit will complete a 12 week off-treatment follow-up period for assessments including safety and anti-drug antibodies. Subjects who complete the planned treatment period may be eligible to enroll in a separate extension study (these patients will not attend the Follow-up visits at Week 58 and Week 64). Subjects who discontinue IP during the study will be encouraged to undergo appropriate study visits/procedures for the full 52-week period (see section 7.1.1).

Please note: If subjects are unable to come to the site during the COVID-19 pandemic, please refer to [Appendix I](#) for further guidance.

Independent Adjudication Committee

An independent adjudication committee will be constituted to provide an external independent assessment of blinded data during the Phase 3 trials to confirm the diagnosis of: 1) MACE (Major Adverse Cardiac Events) (will be defined in the charter) and 2) investigator reported malignancies that occur from randomization until the end of the follow up period.

This independent adjudication committee, will also evaluate cases of ER or urgent care visits and hospitalizations that occur from randomization up to the end of treatment period, as well as all deaths from randomization until the end of the follow up period to evaluate whether any such event is due to a worsening of asthma. The committee will include specialists in pulmonology, cardiology, neurology and oncology and will operate in accordance with dedicated Adjudication Committee Charter/Manual of Operations.

Data Safety Monitoring Board:

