1. Allow the vial to equilibrate at room temperature (about 30 minutes to 1 hour). Ensure that the vial is adequately protected from light during the warming process. Gently swirl the vial to ensure the contents are mixed to a clear, homogeneous solution. Do not shake.
2. To prepare IP for administration remove the tab portion of the vial cap and clean the stopper with 70% ethyl alcohol or equivalent.
3. Attach a 21G 1½-inch sterile disposable needle to a 2mL or 3mL sterile syringe.
4. Withdraw 1.9 mL of the IP from the vial.
5. Remove and discard the 21G 1½-inch sterile disposable needle from the syringe.
6. Attach a new 27G ½-inch sterile disposable needle to the same syringe in step 5.
7. Apply the appropriate label to the syringe.

The assigned vial should be used at one time to prepare the dose required at each visit. Unused product in opened and dispensed vials should not be used for subsequent dosing and should be stored for IP accountability. If the opened and dispensed vials must be discarded immediately after dose preparation as per site’s SOP, the kit boxes must be retained for IP accountability.

The IP will be administered by one SC injection (see [Table 5](#)) and must be prepared using disposable plastic syringes and aseptic technique.

Table 5 Investigational Product Dose Preparation

Dose	Number of vial(s) required	Syringe size required	Total volume administered
210 mg ^a	1	2mL or 3 mL	1.9 mL
Placebo	1	2mL or 3 mL	1.9 mL

[figure not shown]
^a Due to the gradations available on 2 mL or 3 mL disposable plastic syringe, dose based on 1.9 mL administered volume is 209 mg.

Dose Administration

IP will be administered by a qualified healthcare professional (e.g., pharmacist or study nurse) at the site. The injection site must be recorded in the source documents at each treatment visit and in the eCRF. The person administering the dose will wipe the skin surface of the upper arm, anterior thigh or abdomen with alcohol and allow to air dry. The skin will be pinched to isolate the SC tissue from the muscle. The needle will be inserted at a 90 degree angle approximately

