halfway into the SC tissue. The IP will be slowly injected (at least 5 second duration is recommended) into the SC tissue using gentle pressure. The area should not be massaged after injection. It is advised that the site of injection of IP be rotated such that the subject receives IP at a different anatomical site at each treatment visit. In cases when rotation of the injection site is not feasible and/or the subject prefers not to rotate injection sites, the reason for not rotating the injection site should be documented in the source documents. The suggested injection site rotation sequence is presented below in [Figure 2](#).

Figure 2 Suggested schema of Rotation of Injection Sites

Subjects should be observed for a minimum of 2 hours after administration of the first two IP administrations for the appearance of any acute drug reactions. For the remaining doses, subjects will be observed for a minimum of 1 hour after IP administration for any such reaction.

If any of the following should occur, the IP should not be administered:

- The subject received allergen immunotherapy injection on the same day as scheduled IP administration.
- The subject has an intercurrent illness that in the opinion of the investigator and/or medical monitor may compromise the safety of the subject in the study (e.g., viral illnesses).
- The subject is febrile ($\geq 38^{\circ}\text{C}$; $\geq 100.4^{\circ}\text{F}$) within 72 hours prior to IP administration.

The visit should be rescheduled within the allowed visit window and IP should be administered at that visit. If this is not possible the IP administration should be skipped. If a subject skips 2 consecutive IP administrations, the AZ study physician should be contacted to discuss further participation.

If the subject reports an injection site reaction, the investigator or qualified designee will complete the AE eCRF page and an additional eCRF page with questions about the injection site reaction.

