6.4 Treatment compliance

Any change from the dosing schedule or dose discontinuations should be recorded in the eCRF.

The IP Storage Manager is responsible for managing the IP from receipt by the study site until the destruction or return of all unused IP. The date and time of all IP administrations, as well as any missed doses, should be recorded in the appropriate section of the eCRF.

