The study will consist of a screening/run in period between 5-6 weeks, a planned treatment period of 52 weeks and a post-treatment follow-up period of 12 weeks. The follow-up period may not apply to subjects who participate in the extension study. Any data collected after a subject is enrolled in the extension study will not be included in the analyses described in this SAP.

During the planned treatment period, investigational product (IP) will be administered Q4W starting at the randomisation visit (Week 0; Day 1), with the last administration occurring at Week 48. IP will not be administered at Week 52. Subjects who prematurely discontinue IP will be encouraged to remain in the study and undergo appropriate study visits/procedures for the full planned 52-week treatment period, despite no longer receiving treatment. At the IP Discontinuation (IPD) visit, the subject will be given the following 3 options (further details are given in the CSP Section 7.1.1):

1. The subject should be encouraged to return for all regular clinic visits and perform all scheduled assessments until he/she completes a total of 52 weeks in the study (the planned treatment period)
2. The subject will be offered follow-up on a monthly basis via telephone calls while continuing eDiary and PEF completion (no further procedures will be performed), until the subject completes 52 weeks in the study
3. If the subject cannot or does not wish to comply with either of the options above (or any component of them, such as only telephone-based visits without completion of the eDiary and PEF), then the investigator will only contact the subject at 52 weeks post-randomisation. No study assessments will be performed prior to this contact.

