4.2.8.1 Adverse events

AEs will be summarised separately for the on-treatment and on-study periods as defined in [Section 3.1.4](#) unless stated otherwise. All AE summaries will be presented by treatment group. AEs occurring during the screening/run-in period, or occurring post-treatment will be listed, but not summarised separately.

An overall summary table will be produced showing the number and percentage of subjects with at least one AE in each of the following categories: any AEs, serious adverse events (SAEs), AEs with a fatal outcome, AEs leading to discontinuation of IP (DAEs), and adverse events of special interest (AESIs). The total number of AEs in the different AE categories will also be presented as well as the number of subjects (i.e. accounting for multiple occurrences of the same event in a subject).

All AEs will be summarised by system organ class (SOC) and preferred term (PT) assigned to the event using the MedDRA dictionary. For each PT, the number and percentage of subjects reporting at least one occurrence of the event will be presented (i.e. subjects with multiple occurrences of the same PT will only be counted once).

Similar summaries by SOC and PT will also be presented for:

- SAEs
- Fatal AEs
- DAEs
- DAEs causally related to IP
- SAEs leading to discontinuation of IP

- Each AESI category separately
- The most common AEs (defined as those occurring in >3% of subjects in either treatment group) – by PT only

All AEs (by PT) will be summarised additionally by causality and maximum intensity. If a subject reports multiple occurrences within each SOC and PT, the maximum intensity will be taken as the highest recorded (the order being mild, moderate and severe) respectively.

In addition, each AESI category will be summarised by causality.

The AESI of injection site reactions will be further summarised by:

- Site of injection (arm, thigh, abdominal wall)
- Total number of doses administered (1, 2, ..., 13), irrespective of timing of the injection site reaction event.

Exposure-adjusted AE summaries will be presented by SOC and PT for each of the following (on-treatment summaries only):

- All AEs
- Each AESI separately

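### Tabulating injection site reactions by total doses received says almost nothing about when in dosing they occur, and low-total rows could be enriched by selection

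*SAP*

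**What the plan says.** SAP 4.2.8.1 adds two breakdowns for injection site reactions: by site (arm, thigh or abdominal wall) and by the subject's total dose count (1 to 13), "irrespective of timing of the injection site reaction event". It states no denominator for either.

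SAP 8.1.6 defines the event as a subject-level flag: at least one qualifying event with onset in the study period being analysed. The other planned summaries of this event are by system organ class and preferred term, by causality, and as an exposure-adjusted rate per arm. Events leading to discontinuation of treatment are tabulated by system organ class and preferred term. No planned summary gives the dose number or the time from dose to onset.

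The data for such a summary exist:

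- **Doses:** Protocol 6.4 says "The date and time of all IP administrations, as well as any missed doses, should be recorded".
- **Onset:** Protocol 8.3.4 collects start and stop dates for every adverse event.
- **Site:** Protocol 6.2 says "The injection site must be recorded in the source documents at each treatment visit and in the eCRF", and requires an extra eCRF page for each injection site reaction.

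**The concern.** The row a subject falls into is the final dose count, which is usually settled after the reaction. That raises two difficulties.

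First, a first-dose reaction and a thirteenth-dose reaction in two completers land in the same row. The table therefore says little about whether reactions cluster on first exposure, stay constant or build up with repeated dosing, which is what a reader would naturally look for in a breakdown by dose count.

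Second, the outcome may determine the row. A subject who stops because of a reaction after dose 2 is filed under two doses, so constant risk could look like an early-dose hazard. With no reaction-driven stopping, the percentage instead rises with the total simply because subjects with more injections have more chances to react.

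At stake is the interpretability of one safety table for a protocol-defined event of special interest.

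**Working it through.** **Number of rows.** The Protocol synopsis says "IP will be administered from Day 0 until week 48", and SAP 1.2 describes dosing every 4 weeks "with the last administration occurring at Week 48". Doses = 48/4 + 1 = 13, matching the SAP's rows.

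**Inputs.** 530 subjects per arm and 10% dropout, uniform over the study, come from Protocol 9.2. That 10% is study dropout; using it as the background rate of stopping treatment is an assumption. The documents give no reaction risk and no rate of stopping after a reaction, so those values are assumed. No doses are skipped, and each row's denominator is taken as the subjects with that total.

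Background stopping probability after each of doses 1 to 12: b = 1 − 0.9^(1/12) = 0.00874. The 13-dose row then holds 0.9 × 530 = 477 subjects. Rows 1 to 12 share 53, about 4.4 each on average.

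**Check 1: timing, with no reaction-driven stopping.**

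- Early pattern (2% at doses 1-2, then 0.2%): 13-dose row = 1 − 0.98² × 0.998¹¹ = 6.05%.
- Late pattern (0.2% at doses 1-11, then 2%): 13-dose row = 1 − 0.998¹¹ × 0.98² = 6.05%.

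The row holding 90% of subjects is identical under opposite patterns.

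A more extreme contrast fixes a completer's cumulative risk at 5% and spreads the 10% who stop evenly over totals 1 to 12. The 13-dose row then has 477 × 0.05 = 23.85 expected reactors in every case. Rows 1 to 12 combined (53 subjects) have:

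| Pattern | Expected reactors, rows 1-12 |
|---|---|
| All reactions after dose 1 | 53 × 0.05 = 2.65 |
| Constant per-dose risk, 1 − 0.95^(1/13) = 0.39% | 1.34 (sum over k = 1 to 12 of 4.42 × [1 − 0.95^(k/13)]) |
| All reactions after dose 13 | 0 |

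All the information on timing rests on a difference of at most about 2.7 expected subjects, spread over 12 rows.

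**Check 2: more injections, more chances.** With a flat 0.5% per dose and no reaction-driven stopping, the one-dose row is 0.5% and the 13-dose row is 1 − 0.995¹³ = 6.3%. The rise reflects the number of injections, not a change in risk.

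**Check 3: stopping after a reaction.** Keep the flat 0.5% per dose and let a proportion s stop because of a reaction.

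- One-dose row = 0.005[1 − (1 − s)(1 − b)] / {0.005[1 − (1 − s)(1 − b)] + 0.995b}
- 13-dose row = 1 − 0.995 × [0.995 / (1 − 0.005s)]¹²

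| s | One-dose row | 13-dose row |
|---|---|---|
| 0 | 0.5% | 6.3% |
| 20% | 0.00103 / (0.00103 + 0.00870) = 10.6% | 1 − 0.995 × (0.995/0.999)¹² = 5.2% |
| 50% | 0.00252 / (0.00252 + 0.00870) = 22.5% | 1 − 0.995 × (0.995/0.9975)¹² = 3.5% |

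The same constant per-dose risk gives an upward or a downward gradient depending only on s.

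**Check 4: the alternative.** Reactions following dose k, divided by subjects who received dose k, estimate the per-dose risk directly. In a simulation of 2,000,000 subjects this recovered the flat, early and late patterns to within simulation error, with s at 0, 20% or 50%.

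**The case against.** The SAP labels the table as ignoring timing, so it makes no timing claim and readers are warned. Protocol 9.4.4 asks only that events of special interest be summarised descriptively by treatment group. With no denominator stated, the table may simply describe how many doses affected subjects went on to receive. Dose dates and times are listed (SAP 4.2.3), so timing can be reconstructed subject by subject, and the discontinuation tables show how many reactions led to stopping. This stands as a reason to treat the point as minor and to keep the label if the table is kept. It does not supply a summary of timing, which no other planned output provides.

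Several stronger readings are tempting but not supported:

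- **That the table can carry no timing information.** Rows 1 to 12 do differ in principle between patterns (2.65 against 0 expected reactors above). They are too small to be useful.
- **That reactions will cause stopping.** Protocol 7.1 allows stopping for an adverse event or by subject decision, but an injection site reaction is not a listed study-specific criterion and no rate is given.
- **That every total below 13 means stopping.** Protocol 6.2 allows doses to be skipped, and SAP Appendix 8.4 plans summaries of doses missed because of COVID-19. Low rows may include subjects who stayed on treatment.
- **That the by-site summary uses the wrong denominator.** The SAP states none.
- **That sites necessarily alternate.** Protocol 6.2 only advises rotation so that the "subject receives IP at a different anatomical site at each treatment visit", and allows for subjects who do not rotate.

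**Conclusion.** The point holds as a minor improvement. Grouping by final dose count makes this breakdown uninformative in practice about early versus repeated dosing, provided most subjects receive all 13 doses. That loss does not depend on reaction-driven stopping. Selection into low-total rows is conditional on some reactions leading to stopping. Its direction follows from the grouping rule; the 10.6% and 22.5% figures rest wholly on assumed risks and stopping rates.

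A reader might infer that the injection site reaction comparison between arms is biased. It is not: the summaries by system organ class and preferred term, by causality and by exposure-adjusted rate do not use this grouping. No efficacy result, hypothesis test or error rate is touched.

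**What to change.** In SAP 4.2.8.1, add (or substitute) a summary that assigns each injection site reaction to the ordinal number of the most recent dose on or before its onset date. Report the number and percentage of subjects with a reaction at each dose number, by treatment group, with subjects who received that dose as the denominator. If the total-dose table is kept, keep its statement that timing is ignored and state its denominator. For the by-site summary, specify injections given at that site as the denominator.

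The cost is a short SAP wording change and the programming of one or two tables. No new data collection is needed.

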4.2.8.2 Laboratory data

All continuous laboratory variables will be summarised by absolute value at each visit by treatment group, together with the corresponding changes from baseline. These summaries will be produced for the on-study period, as defined in [Section 3.1.4](#). The summary statistics presented will be the minimum, 1st quartile, median, 3rd quartile, maximum, mean and SD.

Central laboratory normal reference ranges will be used for the identification of individual clinically important abnormalities. A shift table will be produced for each laboratory variable to display low, normal and high values. The shift tables will present baseline and maximum/minimum/last post-baseline values for each variable.

Shift plots showing each individual subject's laboratory value at baseline and at maximum/minimum/last value post-baseline will be produced for each continuous laboratory variable. If any laboratory variables show any unusual features (high or low values or a general shift in the data points) at other time points, then shift plots of these data may be produced. The diagonal line of no change will also be displayed on the shift plots.

Both shift tables and shift plots will be produced using all data for the on-study period, as defined in [Section 3.1.4](#).

The frequencies of clinically noteworthy values (using normal reference ranges) occurring during the study will also be given.

In order to identify potential Hy's Law cases, maximum post-baseline TBL will be plotted separately against both maximum post-baseline ALT and AST, expressed as multiples of ULN. These plots will be produced on a log scale, with reference lines included at 2xULN for TBL, and at 3xULN for both ALT and AST. These plots will be produced using all data for the on-study period.

For all subjects who meet the biochemical criteria for Hy's Law (potential Hy's Law cases), the relevant laboratory variables will be tabulated showing all visits for these subjects. Subjects with elevated ALT or AST in addition to elevated TBL at any time may be explored further graphically using individual subject profile plots.

For urinalysis data, a shift table will be generated to present changes from baseline to maximum/last value post-baseline. All data for the on-study period will be used.

All summaries and figures will report laboratory data in SI units.

4.2.8.3 Vital signs

All vital signs variables will be summarised by absolute value at each visit by treatment group, together with the corresponding changes from baseline. This will also include weight, BMI and height (for adolescents only). These summaries will be produced for the on-study period, as defined in [Section 3.1.4](#). The summary statistics presented will be the minimum, 1st quartile, median, 3rd quartile, maximum, mean and SD.

AZ-defined reference ranges (see [Section 3.3.5](#)) will be used for the identification of individual abnormalities. A shift table will be produced for each vital signs variable to display low, normal and high values. The shift tables will present baseline and maximum/minimum/last post-baseline values for each variable.

Shift plots showing each individual subject's vital signs value at baseline and at maximum/minimum/last value post-baseline will be produced for each continuous vital signs variable.

Both shift tables and shift plots will be produced using all data for the on-study period, as defined in [Section 3.1.4](#).

Subjects who have changes from baseline outside the pre-defined AZ clinically important change criteria in [Section 3.3.5](#) will be summarised. All data for the on-study period will be used.

4.2.8.4 12-lead digital ECG

Continuous 12-lead ECG variables will be summarised by absolute value at each visit by treatment group, together with the corresponding changes from baseline. These summaries will be produced for the on-study period, as defined in [Section 3.1.4](#). The summary statistics presented will be the minimum, 1st quartile, median, 3rd quartile, maximum, mean and SD.

A shift table will be produced to display the investigator assessment of normal, abnormal – not clinically significant, abnormal – clinically significant and not done between baseline and end of study. For this purpose, borderline (also recorded on the eCRF) will be grouped with normal.

A frequency table showing subjects with Fredericia corrected QT (QTc) values and increases from baseline at any time during the on-study period using standard pre-specified thresholds will be produced.

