- ^w Subjects completing the EOT period, may be eligible to enroll in a separate extension study D5180C00018 and that these subjects will not complete the follow-up visits at Week 58 and Week 64. During the Corona Virus Disease 2019 (COVID-19) pandemic, subjects enrolling in the separate extension study D5180C00018 will continue participation in the follow-up visit(s) (Week 58, Week 64) until the on-site visit (or alternate site) for extension study randomization and IP administration can be conducted.

EOT End-of-Treatment; FU Follow-up; IPD Investigational Product Discontinuation; UNS Unscheduled; W Week.

CHANGES REQUIRED DURING THE COVID-19 PANDEMIC

Please Note: Changes below should only be implemented during the COVID-19 pandemic.

During the COVID-19 pandemic, changes are being implemented in order to ensure the safety of study subjects, to maintain compliance with good clinical practices, and to minimize risks to data integrity. Where allowable by local health authorities, ethics committees and healthcare provider guidelines (e.g. hospital policies), these changes include:

- The option of home visits including home administration of Investigational Product (IP) performed by a qualified Health Care Professional (HCP). Additional information related to the visit can be obtained remotely by phone call and/or video conference. The rationale for this change is to minimize the risk of subjects missing scheduled IP administration and visit assessments due to inability/unwillingness to visit the site during the COVID-19 pandemic.
- Remote visits (phone call and/or video conference) to replace on-site visits, if subjects cannot attend the visits at the study site,

at an alternate site or have home visits. The rationale for this change is to ensure that assessments and collection of information continue for visits that cannot be done at the site, at an alternate site or at the subject's home. This will reduce the risk of subject exposure to COVID-19

- Subjects aimed to transition to the extension study D5180C00018 to continue participation in the safety follow-up visit(s) (Week 58, Week 64) until the on-site (or alternate site) extension study randomization and IP administration can be conducted. The rationale for this change is to ensure randomization/first IP administration in the extension study D5180C00018 can be performed at the site (or alternate site) and to increase the chances of subjects transitioning to the extension study.

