The study is designed to dose subjects at Q4W with the last dose given at week 48, EOT visit at week 52, and a 12-week follow-up period.

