4.4 End of study definition

The end of study is defined as when the last subject has completed his/her last scheduled contact.

A subject is considered to have completed the study when he/she has completed his/her last scheduled contact.

See Appendix [A 6](#) for guidelines for the dissemination of study results.

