5.3 Lifestyle restrictions

Subjects must abstain from donating blood and plasma from the time of informed consent, and for 16 weeks (5 half-lives) after last dose of IP.

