7.1.1 Procedures for discontinuation of study treatment

Subjects are free to discontinue IP or withdraw from the study at any time without prejudice to further treatment. Discontinuing study treatment is not the same as study withdrawal. Procedures to follow for study withdrawal are detailed below in section 7.3. If the subject decides to withdraw consent, then the reason for this must be recorded separately in the eCRF.

A subject that decides to discontinue IP should always be asked about the reason(s) and the presence of any adverse events. The reason for discontinuing treatment and the date of last IP administration should be recorded in the eCRF. Subjects permanently discontinuing IP administration should be given locally available standard of care therapy, at the discretion of the Investigator. However, treatment with marketed or investigational biologics is not allowed until week 64 even if the subject has discontinued IP. Interaction studies between tezepelumab and other biologics indicated for the treatment of asthma have not been conducted. For additional information regarding pharmacokinetic and pharmacodynamic effects of tezepelumab reference should be made to the investigator brochure.

All subjects who prematurely discontinue IP should return to the study center and complete the procedures described for the premature IP Discontinuation visit (IPD) at 4 weeks (+/-5 days) post last IP administration. Subjects who discontinue treatment should be encouraged to return for all regularly scheduled visits for safety and efficacy assessments.

At the IPD visit the subject will be given three options as to how they will be followed as follows:

1. The subject should be encouraged to return for all regular clinic visits and perform all scheduled assessments until he/she completes a total of 52 weeks treatment period.
2. The subject will be offered follow-up on a monthly basis via telephone calls while continuing diary and ePEF completion (no further procedures will be performed), until the subject completes 52 weeks in the study. In addition to the PRO assessments that are performed at home, the subject may also complete the other clinic specified PRO assessments (as defined in the SoA) at home as well. The subject should return for a follow-up visit 16 weeks (+/- 5 days) (refer to SoA, V19 – Week 64) post last IP administration and for the EOT visit at Week 52 (+/-5 days).

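### The SAP tabulates the investigator's ECG assessment only as a shift from baseline to an undefined end of study, so an earlier abnormality that has resolved by then does not appear in that table

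*SAP*

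**What the plan says.** SAP 4.2.8.4 plans three ECG outputs:

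- by-visit descriptive statistics for the continuous variables;
- a frequency table of QTc values and increases at any time on study;
- one shift table of the investigator's assessment, with categories ending "clinically significant and not done between baseline and end of study". Borderline is grouped with normal.

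The schedule of activities (Protocol 1.1, Table 2) places ECGs at Weeks 0, 24, 52 and 64 and at the IP discontinuation visit.

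For laboratory variables, SAP 4.2.8.2 says: "The shift tables will present baseline and maximum/minimum/last post-baseline values for each variable". SAP 4.2.8.3 uses the same rule for vital signs, and urinalysis uses maximum and last.

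Protocol 9.4.4 commits to summarising ECGs that the investigator interprets as abnormal. It does not restrict this to the final ECG.

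**The concern.** The table has one post-baseline column per subject, and the SAP does not say which ECG fills it. If it is the last ECG, subjects who complete follow-up are represented by a tracing taken after washout, and their on-treatment assessments at Weeks 24 and 52 are not used.

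Digital ECG is a named safety endpoint and major adverse cardiac events are adjudicated. A reader will therefore look to this table for the investigator's judgement on tracings obtained during treatment. A clinically significant abnormality at Week 24 or Week 52 that had cleared by the final tracing would be counted there as normal.

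**Working it through.** **Inputs**

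- Last dose: SAP 1.2, "with the last administration occurring at Week 48"; target day 337 (SAP Table 1).
- Week 52 target day 365; Week 64 target day 449, window 428–469 (SAP Table 1).
- Safety on-treatment period ends 33 days after the last dose, or at earlier death or withdrawal (SAP 2.1.5).
- Half-life: Protocol 5.3 sets a restriction "for 16 weeks (5 half-lives) after last dose of IP".
- Subject completion: Protocol 4.4, "A subject is considered to have completed the study when he/she has completed his/her last scheduled contact".
- Extension entrants: Protocol 1.1, Table 2, footnote w, "these subjects will not complete the follow-up visits at Week 58 and Week 64". The same footnote keeps them in follow-up visits during the pandemic until on-site extension randomisation is possible.

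**Timing of the Week 64 ECG**

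- The documents' own interval is reproduced: 449 − 337 = 112 days = 16 weeks. Protocol 7.1.1 likewise places Visit 19 "16 weeks (+/- 5 days) (refer to SoA, V19 – Week 64) post last IP administration".
- Across the analysis window: (428 − 337)/7 = 13.0 weeks to (469 − 337)/7 = 18.9 weeks.
- On-treatment cut-off: 337 + 33 = day 370. The target Week 64 ECG is 449 − 370 = 79 days beyond it.
- Implied half-life: 112/5 = 22.4 days. Assuming simple exponential decline, 2^(−5) = 0.031, so about 3% of drug remains.
- The Week 52 ECG is 365 − 337 = 28 days after the last dose. It is on-treatment, with 2^(−28/22.4) = 0.42 remaining on the same assumption.

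**What the table shows under each reading of end of study**

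| Reading | Completes follow-up | Enters extension | Not visible in this table |
|---|---|---|---|
| Last available ECG | Week 64, off treatment | Normally Week 52, on treatment; later under the COVID-19 provision | Any abnormality resolved by that ECG; on- and off-treatment tracings share one column |
| Fixed Week 64 visit | Week 64, off treatment | Normally no ECG | Resolved Week 24 and Week 52 findings; most extension entrants |
| Fixed Week 52 visit | Week 52, on treatment | Week 52, on treatment | Resolved Week 24 findings; anything first seen at Week 64 |

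The first reading is the most natural. The SAP's abbreviation list separates End of Study from End of Treatment, and Protocol 4.4 ties completion to the last scheduled contact. Subjects who stop IP early add to the mixture, because their follow-up visit is 16 weeks after their own last dose.

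None of the three readings yields the worst post-baseline assessment. A maximum or worst-value rule, as used for the laboratory and vital-sign tables, would.

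**The case against.** The strongest objection is that the washout argument depends on an undefined term. Protocol 4.4 defines completion, not an ECG analysis time point. The 'not done' category also fits a fixed visit at least as well as a last-available value, and a fixed Week 52 visit would be on-treatment for everyone who completes dosing. This stands: the Week 64 interpretation is the likeliest, but it is not certain.

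It is also fair to say that the ECG is not otherwise neglected:

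- SAP 4.2.8.4 gives minimum, quartiles, median, maximum, mean and SD at each visit for the continuous variables, and QTc outliers at any time.
- SAP 3.1.5 says that listings cover scheduled and unscheduled visits.
- A new clinically significant finding may be reported as an adverse event, and adjudicated cardiac events are summarised.
- The Protocol 9.4.4 commitment is not withdrawn in SAP Section 6.

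A reader might infer that ECG findings on drug go unreported, or that a cardiac signal is being hidden. The documents support neither. The outputs above remain, and Protocol 2.2 and 2.3 describe no safety signal to date.

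These routes do not replace the missing table, however. Continuous summaries and QTc thresholds do not carry the investigator's overall judgement. Protocol 8.3.7 has no specific rule making every investigator-assessed ECG abnormality an adverse event. For physical examination, by contrast, SAP 4.2.8.5 omits a summary precisely because those findings go through adverse event reporting; it says nothing similar for ECG.

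**Conclusion.** The point holds for one table. The only planned tabulation of the investigator's categorical ECG assessment uses a single undefined end time point, and on every reading it can count a resolved earlier abnormality as normal. This departs from the SAP's own rule for laboratory and vital-sign shift tables, and no reason is given.

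The further conclusion, that the time point is a washed-out ECG 16 weeks after the last dose, applies to subjects who complete follow-up and rests on reading end of study as the last ECG. It does not extend to everyone: extension entrants normally end at Week 52, within the on-treatment period, unless the COVID-19 provision keeps them in follow-up.

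The number of subjects affected cannot be given, because the documents state neither the share entering the extension nor the frequency of transient ECG abnormalities. No efficacy result or hypothesis test is touched. The change is worth making because the present rule gives a less informative safety summary from data already collected.

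**What to change.** In SAP 4.2.8.4, replace or supplement the current table with a shift from baseline to the worst post-baseline investigator assessment, ordered normal/borderline < abnormal not clinically significant < abnormal clinically significant. Present it for the on-treatment period (Section 2.1.5) and for the on-study period (Section 3.1.4). If the end-of-study shift is kept, define it as the last available post-baseline ECG.

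SAP 3.3.6 already takes the overall evaluation and clinical significance from the eCRF, so no new data are needed. The cost is a wording change and one reprogrammed descriptive table.
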